1.1.7 Visit Schedule

For each subject, the study consists of assessments preoperatively, immediately after operation and the follow up visits postoperatively. The recommend time window of scheduled visits is ± 7 days. The clinical assessments and procedures performed at each visit are shown in Table 2.

Clinical Investigation Plan

Bioabsorbable Intramedullary Nail Fixation of Forearm Fractures in Children

During these visits will be investigated: function of both arms, radiological fracture healing, well-being and incidence of complications.

Table 2 Assessment and procedures at each visit

Assessment	Operation		4 week	12 weeks	26 weeks	52 weeks	104 weeks
	Pre-operative	Post-operative					
	Visit 1	Visit 2	Visit 3	Visit 4	Visit 5	Call 6	Visit 7
Informed consent, inclusion and exclusion criteria	X						
Demographics, medical history	X						
Injuries and comorbidities	X						
Randomization	X						
Fracture reduction and fixation	X						
Cast removal			X				
TEN nail removal					X		
Primary performance variable	Operation		4 week	12 weeks	26 weeks	52 weeks	104 weeks
	Pre-operative	Post-operative					
	Visit 1	Visit 2	Visit 3	Visit 4	Visit 5	Call 6	Visit 7
Functional and clinical outcome evaluated by measuring rate of motion			X	X	X		X
Pain assessment		X	X	X	X	X	X
Subjective		X	X	X	X	X	X

Clinical Investigation Plan

Bioabsorbable Intramedullary Nail Fixation of Forearm Fractures in Children

result							
Secondary variables	Operation		4 week	12 weeks	26 weeks	52 weeks	104 weeks
	Pre-operative	Post-operative					
	Visit 1	Visit 2	Visit 3	Visit 4	Visit 5	Call 6	Visit 7
Radiographic outcome and bone union formation evaluated by plain radiographs	X	X	X	X	X		X
Radiographic outcome and bone union formation evaluated by MRI imaging		X*		X*		X*	X*
Safety and tolerability variables	Operation		4 week	12 weeks	26 weeks	52 weeks	104 weeks
	Pre-operative	Post-operative					
	Visit 1	Visit 2	Visit 3	Visit 4	Visit 5	Call 6	Visit 7
Adverse events	X	X	X	X	X	X	X
Concomitant medications	X	X	X	X	X	X	X
Conclusion of participation							X

* Radiographic outcome and bone union formation of 5-10 subjects will be evaluated by MRI imaging immediately after operation and three follow up visits

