1.1.14 Other Variables

Other variables documented in CRF are:

- Operation time
- Number of days lost from usual activities
 - Parents lost working days
- Length of hospitalization stay
- Complaints in daily living
- Esthetics

Statistics

Recommended statistical methods will be applied. All deviations made after approval of the CIP will be described and justified in the final study report.

Sample Size Considerations

Primary outcome variable in this study is loss of supination and pronation within 6, 12, 26, 52, and 104 weeks after surgery. The non-inferiority margin is set to be 80 % in the calculations (=Power).

It is previously known that the forearm pronation in this age group is 81.2 degrees (95% CI 79.6-82.28) and 79.6 degrees (95% CI 78.8-80.4) in girls and boys, respectively. The corresponding supination archs are 90.0 degrees (95% CI 88.0-92.0) and 87.8 degrees (95% CI 85.7-89.9). [26] The standard deviation (SD) is 6.1 degrees in pronation and 7.6 degrees in supination. We determined that the new method (ActivaNail –intramedullary fixation) should

Clinical Investigation Plan

Bioabsorbable Intramedullary Nail Fixation of Forearm Fractures in Children

result to the forearm rotational range of motion that is not more than 15 degrees lower, compared to the rotational range of motion in TEN group, according to the Price's classification (<15 degrees of decrease refers to excellent outcome).

Difference between means in the groups is set as 7.0 and the Alpha as 0.05. The sample size is estimated to be 13 experimental subjects and 13 controls according to an unpaired two sample Student t test. This study population will also be exclusively large enough to recognize decrease in the ROM that is clinically significant (>15 degrees of decrease in supination or pronation in ActivaNail compared to TEN group).

Statistical Hypothesis

The following hypothesis will be tested for the primary efficacy variable:

H₀: Investigational device is inferior to comparative devices

H₁: Investigational device is non-inferior to comparative devices

The non-inferiority limit is set to 80 %. Thus, non-inferiority is shown if the upper limit of the 95% confidence interval for the difference is less than or equal to 5 %.

Statistical Methods

All operated subjects who reach the 2-year follow-up will be included in the statistical analysis. Study data will be tabulated by treatment groups with descriptive summary statistics.

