The conventional level of 5% will be considered the level of statistical significance. All tests will be two-sided. Accordingly, 95% confidence intervals will be used.

Normality assumptions will be checked using normal probability plot for residuals. The use of transformation for a particular variable will be decided after examining the assumptions with the original scale of measurement. Analysis may be repeated without possible outliers.

The primary variable will be analyzed using an analysis of variance model for repeated measurements. Treatment differences with 95% confidence intervals will be calculated from the model. If the assumptions for the parametric models are not met suitable non-parametric models will be used.

Clinical Investigation Plan

Bioabsorbable Intramedullary Nail Fixation of Forearm Fractures in Children

Adverse Events

The safety variables to be evaluated include adverse events (AE), findings from physical and radiographic examinations, subjective reports of pain and functional outcome assessments. Further, all drop-outs will be reported. The adverse event data will include the following displays:

- AEs categorized by body system
- AEs categorized by severity grades 1-4 (mild, moderate, severe, life-threatening)
- AEs involving the region under study (RUS) specifically:
 - Fracture delayed union, nonunion and malunion
 - Hardware failure
 - Infection

All Serious Adverse Events (SAE) will be reported within 24 hours to the Sponsor. The SAEs include death, life-threatening event, medically important event, device malfunction, hospitalization, accidental exposure, persistent disability or incapacity, and cancer. In emergency SAE cases, the patients are requested to seek help in the Emergency room of the University Central Hospital. Any adverse events and their effects are reported using Case Report Form (CRF).

Quality Management

Monitoring Arrangements

The sponsor is responsible for the monitoring of this study. The principal investigator will provide sponsor with the data recorded during the study without personal identification data to allow the sponsor to check the compliance of the study with the CIP. The sponsor will appoint a monitor for assessing the investigator's compliance with the Clinical Investigation Plan and for performing source-data verification. A monitoring plan and report will be prepared.

Data Management

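### The deciding confidence interval comes from a repeated-measures ANOVA with no visit named, so it may not answer the two-year question, or may do so with error pooled from earlier visits

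*Protocol*

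**What the plan says.** Protocol, Statistical Methods (10.3): "The primary variable will be analyzed using an analysis of variance model for repeated measurements". The next sentence takes the treatment differences and their 95% intervals from this model, and the Synopsis repeats both statements. Neither place gives the visit, the contrast, the error term or the covariance structure. The non-inferiority rule in Statistical Hypothesis (10.2) rests on a 95% interval and also names no visit.

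Other parts of the Protocol point to a single time. The Synopsis sets the primary objective at the two-year follow-up. The analysis set is defined by reaching it: "All operated subjects who reach the 2-year follow-up will be included in the statistical analysis". The sample size rests on one two-group comparison: "The sample size is estimated to be 13 experimental subjects and 13 controls according to an unpaired two sample Student t test".

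In Table 2 (Visit Schedule), the row "Functional and clinical outcome evaluated by measuring rate of motion" is marked at weeks 4, 12, 26 and 104. Week 52 is a call with no motion measurement. Sample Size Considerations (10.1) lists the primary variable at 6, 12, 26, 52 and 104 weeks instead.

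**The concern.** The question asked is how the two devices compare at two years. The model named is one for the whole course of recovery. Unless the visit and contrast are fixed, the ordinary form of that model leads to one of two results:

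- **A group effect averaged over visits.** This has a valid error term but estimates something else. A 7.0-degree deficit present only at week 104 would appear as 7.0/4 = 1.75 degrees in an average over four visits.
- **A week-104 contrast with pooled error.** Its standard error then depends on the spread at weeks 4, 12 and 26. Week 4 is the cast-removal visit in Table 2, so it is reasonable to suspect that spread differs there, although the Protocol gives no figure.

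The classical form also needs every visit to be present. Applied in that way, it would conflict with the statement that all operated children who reach two years are analysed. At stake is whether the primary interval is correctly sized, and for the intended quantity, in a trial planned on 13 per group.

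**Working it through.** **Inputs from the Protocol.** "Difference between means in the groups is set as 7.0 and the Alpha as 0.05". "All tests will be two-sided. Accordingly, 95% confidence intervals will be used". Power is 80% (10.1 labels this figure as the margin but equates it with power). "The standard deviation (SD) is 6.1 degrees in pronation and 7.6 degrees in supination"; these are given alongside reference ranges of motion, one value per movement and none by visit. Minimum 13 per group.

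**Assumptions.** SDs at weeks 4, 12 and 26; 6.1 or 7.6 used as the week-104 SD; correlation between visits of 0.3 to 0.7.

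**1. The plan's own figure.** Normal approximation with SD 6.1: n = 2 × (1.960 + 0.842)² × 6.1² / 7.0² = 11.9, so 12 per group. The exact two-sided t calculation gives 13 per group with 80.1% power, which reproduces 13 + 13. It reproduces with the pronation SD only: SD 7.6 gives 20 per group, and 13 per group then has 61.5% power. In either case the calculation is for one comparison with one SD, not for a repeated-measures model.

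**2. Interval from week 104 alone.** Half-width = t(0.975; 24 df) × SD × √(2/13) = 2.064 × SD × 0.3922. This is 4.94 degrees for SD 6.1 and 6.15 for SD 7.6. The simulated means are 4.9 and 6.1, with 95% coverage.

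**3. Week-104 contrast from the univariate repeated-measures ANOVA.** The variance estimate is (MS_subject + 3 × MS_residual)/4, with Satterthwaite degrees of freedom. Its expectation is the plain mean of the four visit variances, whatever the correlation. With t about 2.00:

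- SDs 15/10/8/6.1: mean variance (225 + 100 + 64 + 37.21)/4 = 106.55, root 10.32, half-width about 2.00 × 10.32 × 0.3922 = 8.1.
- SDs 15/10/8/7.6: mean variance (225 + 100 + 64 + 57.76)/4 = 111.69, root 10.57, half-width about 8.3 by the same formula.
- SDs 3.05/4.27/5.49/6.1 (multiples 0.5, 0.7, 0.9 and 1 of 6.1): mean variance (9.30 + 18.23 + 30.14 + 37.21)/4 = 23.72, root 4.87, half-width about 3.8.

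Simulation with 13 per group and four visits gives:

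| SDs at weeks 4/12/26/104 | Week 104 alone | Pooled error | Coverage, pooled |
|---|---|---|---|
| 6.1 at all visits | 4.9 | 4.7–4.8 | 95% |
| 15/10/8/6.1 | 4.9 | 8.0–8.1 | above 99% |
| 15/10/8/7.6 | 6.1 | 8.2–8.3 | about 99% |
| 20/12/8, then 6.1 or 7.6 | 4.9–6.1 | 9.9–10.1 | above 99% |
| 0.8, 0.9, 1 and 1 × 6.1 | 4.9 | 4.4 | 93% |
| 0.5, 0.7, 0.9 and 1 × 6.1 | 4.9 | 3.8 | 88% |

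At correlation 0.5 the 15/10/8 cases give 8.1 and 8.2. The choice of correlation hardly matters.

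**4. Averaged contrast.** Coverage for the visit-averaged effect is about 95% in every case run. The problem there is the quantity estimated, not its error term.

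**5. Complete cases.** If a proportion p misses each of three earlier visits independently, (1 − p)³ of children remain. At p = 2%, 5% and 10% this is 0.941, 0.857 and 0.729, or 12.2, 11.1 and 9.5 of 13. The Protocol gives no rate of missed visits. On the visit list in 10.1, which includes week 52, a complete-case model would keep no child, because motion is not scheduled at week 52.

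**The case against.** The wording does not fix a univariate ANOVA. It also fits a multivariate or mixed repeated-measures model, and the covariance structure and error term may be set in an analysis plan that is not shown. This stands, and it is why the point is conditional. It does not dispose of the point: the model family and the source of the deciding interval are stated in the Protocol, and neither is tied to the two-year visit that the objective names.

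Three stronger readings are tempting, and the document does not support them.

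- **That the interval is too wide.** This needs larger spread at the early visits. No SD by visit is given, and the 6.1 and 7.6 are not stated to be week-104 values. Equal spread does no harm, and the reverse pattern makes the interval too narrow.
- **That the plan drops children who missed an earlier visit.** It states no such rule. Statistical Methods says that all operated subjects who reach two years are included, so deletion would be a conflict with the text, not a planned exclusion.
- **That nothing but normality is considered.** The residual plot for normality is the only check named, but the section also provides a general non-parametric fallback if model assumptions fail. What remains is that no stated check looks at spread between visits.

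**Conclusion.** The point holds as a mismatch between objective and model, with a conditional consequence for the interval. The objective is at two years, while the deciding interval comes from a repeated-measures ANOVA with no visit or contrast named.

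If the ordinary univariate form is used for a week-104 contrast, the interval is correctly sized only when spread is equal at all visits. With assumed SDs of 15/10/8 at weeks 4, 12 and 26 and 6.1 to 7.6 at week 104, the half-width is about 8.0 to 8.2 instead of 4.9 to 6.1 degrees. With equal SDs there is no harm. With early SDs of 0.5, 0.7 and 0.9 times the week-104 value, coverage is about 88%, which would favour a non-inferiority claim. All sizes rest on 13 per group and on visit SDs that the document does not supply. The change is worth making because it is cheap and removes this dependence, not because an error of known size has been shown.

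**What to change.** In Statistical Methods and in the matching Synopsis text, state that the non-inferiority verdict comes from the treatment difference at week 104. Estimate it in one of two ways:

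- a linear model of the week-104 value; or
- a likelihood-based mixed model with visit-by-treatment terms, unstructured covariance and Kenward-Roger degrees of freedom, reporting the week-104 contrast.

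State that every child with a week-104 value is kept whatever earlier visits were missed, which agrees with the analysis set as written. Report weeks 4, 12 and 26 as recovery curves, and reconcile the visit list in Sample Size Considerations with Table 2.

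The cost is wording in two places and slightly fewer error degrees of freedom. If SDs are equal at all visits, the week-104 interval is about 0.1 degree wider on each side (4.9 against 4.8).

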Closed reduction and plaster cast immobilization provides in most cases of children's forearm fractures sufficient stability for an uneventful healing of the fracture and gives a satisfactory end result. [1-5] The satisfactory results are achieved due to rapid healing and remodelling of angulations in children.

However, in cases of

- unstable fractures (e.g. midshaft diaphyseal forearm fractures),
- fractures with unacceptable alignment and fracture dislocations,
- open fractures,
- segmental fractures,
- proximal fractures that will not remodel as predictably and
- those with associated neurovascular compromise

an operative treatment is often mandatory to avoid residual deformity with permanent loss of forearm rotation. [1, 3, 6-9] Remodeling will not correct rotational deformities of the distal third of the forearm; for that reason, rotational deformities must be often treated operatively. [2] In addition, in an older child ability for fracture remodeling and correction of deformity is not as effective as in a younger child, therefore the operative treatment of displaced forearm fractures is often recommended in children older than 10 years of age and in younger children when conservative treatment fails.

Effective operative alternatives of unstable fractures include open reduction and internal fixation (ORIF) with plates and screws or mini-open reduction and intramedullary (IM) nailing. [1, 8-10] The choice of fixation usually is a matter of surgeon preference.

Plate fixation allows anatomic reduction and early motion with most studies showing good outcomes in the pediatric population. However, plate fixation requires a large surgical approach and smaller children may have bones that are too narrow to accommodate a plate. [8] In addition, incision for a plate fixation is greater than that required for IM nailing. In contrary to TEN nailing if plate fixation is applied the injured area of bone is exposed. This may also have a negative effect on the healing of the fracture by disturbing the haematoma and callus formation and increase complication possibilities, like infection. Plate removal is also associated with significant complications, such as nerve injury, and in addition, the removal of plate may be difficult due to scarring and bone growth over the plates. [9]

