1.1.9 Functional and Clinical Outcome Measurements

Healing of the injury will be clinically monitored using repeated functional measurements, pain assessments and by means of standardized questionnaires. The follow-up will be performed according to table 2. The functional examinations will include the supination and pronation of the forearm, flexion and extension of elbow, dorsiflexion and palmar flexion of the wrist using a goniometer, and their comparison to the corresponding measurements of the subject's healthy forearm.

[figure not shown]

Figure 1 Determination of forearm's pronation and supination angles

In measuring of pronation, the vertical limb of the goniometer is placed parallel to the long axis of the humerus, while the horizontal limb is placed on the back of the wrist (to eliminate additional motion at the radiocarpal joint). In the measuring supination the horizontal limb is placed on the anterior aspect. The average range of pronation/supination is 90/90 degrees (50/50 degrees necessary for activities of daily living). ***Flynn's criteria for elbow assessment is used to evaluate the clinical significance of outcomes (excellent and good comprising satisfactory, and fair and poor comprising unsatisfactory), as well as the classification by Price.***

[figure not shown]

Figure 2 Determination of A) elbow's flexion and extension, B) wrist's dorsiflexion and palmar flexion

Clinical outcome and fracture union will be also assessed by the absence of pain and bony tenderness at fracture site. The subjects will be also asked to perform self-assessment of perceived pain in the region of study using 10 cm visual analogue scale (VAS) as a measure of pain severity.

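### The primary repeated-measures ANOVA names no covariate, although healthy-arm rotation and age are collected; prespecifying both would usually narrow the interval at little cost

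*Protocol*

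**What the plan says.** - **Model.** Statistical Methods (10.3): "The primary variable will be analyzed using an analysis of variance model for repeated measurements". Treatment differences with 95% intervals come from that model. No model terms are listed, and no covariate is named or ruled out.
- **Outcome.** Sample Size Considerations (10.1) and Primary Performance Variable (1.1.11) define the outcome as loss of supination and pronation. Neither says what the loss is measured from.
- **Healthy arm.** Functional and Clinical Outcome Measurements (1.1.9) describes goniometer readings and "their comparison to the corresponding measurements of the" healthy forearm. Visit Schedule (1.1.7) lists "function of both arms, radiological fracture healing, well-being and incidence of complications" among the items examined at visits. Table 2 marks motion at 4, 12, 26 and 104 weeks and at no preoperative visit.
- **Age.** Children aged 5 to 16 are eligible and demographics are recorded. The Literature Review (7.1) says that "in an older child ability for fracture remodeling and correction of deformity is not as effective as in a younger child".
- **Sizing.** "Difference between means in the groups is set as 7.0 and the Alpha as 0.05". SDs are 6.1 degrees (pronation) and 7.6 degrees (supination), with 13 per group from an unpaired t test. Under Statistical Methods, "All tests will be two-sided. Accordingly, 95% confidence intervals will be used".

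**The concern.** The result is read from a confidence interval for a treatment difference with as few as 13 children per group, so any avoidable variance widens the interval that decides it. A child's native rotation, seen in the healthy arm, is an obvious source of between-child variation, and the protocol itself gives a reason to expect age to matter. Both are recorded, but the stated model uses neither explicitly.

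If loss means injured arm minus healthy arm, subtraction fixes the healthy-arm coefficient at 1. That adds noise when the two arms correlate weakly. If loss means something else, the healthy arm has no stated place in the model. Either way, chance imbalance in age or native mobility is left uncorrected in a small trial.

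**Working it through.** **1. The plan's own figure.** For an unpaired t test (noncentral t) with difference 7.0, SD 6.1, two-sided alpha 0.05 and 13 per group, power is 80.1%. The stated 13 is reproduced with the pronation SD. With the supination SD of 7.6, power at 13 per group is 61.5%, and 20 per group would be needed for 80%. The 80% is the power, although the text labels it otherwise ("The non-inferiority margin is set to be 80 % in the calculations (=Power").

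**2. Three ways to treat the healthy arm.** Let s be the SD of motion, equal in both arms (assumed), and rho the injured-to-healthy correlation (assumed; none is given). The variance per child is:

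- ignore: s²
- subtract: 2(1 − rho)s²
- adjust: (1 − rho²)s², times a small-sample factor for estimating the slope. With 26 children and one covariate the factor is 1 + 1/22, on 23 df. With two covariates it is 1 + 2/21, on 22 df.

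**3. Power at 13 per group, difference 7, two-sided 5%, one time point.** The last column adds a second covariate that explains nothing.

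| SD | rho | ignore | subtract | adjust, 1 covariate | adjust, 2 covariates |
|---|---|---|---|---|---|
| 7.6 | 0 | 62% | 36% | 60% | 57% |
| 7.6 | 0.3 | 62% | 48% | 64% | 61% |
| 7.6 | 0.5 | 62% | 62% | 72% | 70% |
| 7.6 | 0.7 | 62% | 83% | 87% | 85% |
| 6.1 | 0.3 | 80% | 66% | 82% | 80% |
| 6.1 | 0.5 | 80% | 80% | 89% | 87% |
| 6.1 | 0.7 | 80% | 95% | 97% | 96% |

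**4. Interval half-width at SD 7.6, rho 0.5.**

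- Ignore or subtract: 2.064 × 7.6 × √(2/13) = 6.15 degrees.
- Adjust, one covariate: 2.069 × 7.6 × √0.75 × √(23/22) × √(2/13) = 5.46 degrees.

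**5. Where adjustment stops paying (variance only).**

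- Against subtracting, one covariate: (1 + rho)(23/22) < 2 requires rho < 44/23 − 1 = 0.91.
- Against subtracting, two covariates with the second uninformative: (1 + rho)(23/21) < 2 requires rho < 42/23 − 1 = 0.83.
- Against ignoring, one covariate: (1 − rho²)(23/22) < 1 requires rho > √(1/23) = 0.21.

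**6. Against the 15-degree limit.** With no true difference, SD 7.6, 13 per group and one rotation direction (noncentral t), power is 99.8% when ignoring the healthy arm. When subtracting it is 98% at rho 0.3 and 93% at rho 0, the worst case examined.

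**The case against.** Covariates are often left to a statistical analysis plan, and none is shown here, so their absence alone is no error. That stands. The point is kept because the protocol itself fixes the outcome, the model family and the source of the interval, and it requires deviations after approval to be justified in the final report.

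Three stronger readings are tempting, and the documents do not support them:

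- **That the plan subtracts the healthy arm, or discards it.** A reader might infer either. Subtraction is the natural reading of loss next to a comparison with the healthy side, but the protocol states neither.
- **That adjusting always wins.** At this sample size it does not win above rho of about 0.9, or below about 0.2 when the alternative is to ignore the healthy arm. Quoting the gain only against subtraction also flatters it: at rho 0.3 and SD 7.6 the gain is 16 points over subtracting but 2 over ignoring.
- **That non-inferiority is in jeopardy without adjustment.** Step 6 shows that it is not, for the 15-degree limit with no true difference.

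Two further points stand. Healthy-arm motion is first recorded after randomisation in an unblinded trial. The implant is unlikely to affect the uninjured arm, but the value must be fixed in advance. Also, 13 per group is a minimum and 35 children are to be enrolled, so the small-sample charge may be somewhat lighter than shown.

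**Conclusion.** The point holds as a precision improvement, not as an error in the plan. For rho between 0.3 and 0.7, adjusting for one healthy-arm value gives more power than either alternative. At SD 7.6 and rho 0.5 it raises power for a 7-degree difference from 62% to 72% and cuts the half-width by 0.69 degrees (6.15 to 5.46).

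The downside is bounded. Near rho 0, adjusting loses about 2 points against ignoring the healthy arm, or about 4 if a second covariate explains nothing. At high rho it merely fails to improve on subtraction. Since rho is unknown, adjustment is the safer choice: subtraction at rho 0 would cost about 26 points (62% to 36%).

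The figures rest on an assumed rho, equal variances in the two arms, the protocol's SDs and a single time point. What is gained is a narrower interval and protection against chance imbalance in age and native mobility.

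**What to change.** In Statistical Methods, specify a repeated-measures model for injured-arm rotation at each motion visit. Its fixed terms are treatment, visit, treatment-by-visit, one healthy-arm rotation value per child, and age. Take the treatment difference in degrees with its 95% interval at 104 weeks.

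Name the healthy-arm value in advance, for example the one from the first motion visit, since none is taken before surgery. State what loss is measured from. If loss is defined as that same healthy-arm value minus injured-arm rotation, entering the value as a covariate gives the same treatment difference with the sign reversed, so the outcome can keep its name and the Price and Flynn gradings are untouched.

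List the motion visits in the model so that they agree with Table 2. The sample-size section names 6 and 52 weeks, whereas Table 2 has motion at 4 weeks and only a call at 52.

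The cost is analysis wording and one or two degrees of freedom out of 24. No new data are needed, and the estimate stays in degrees.
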